4. AMENDMENTS AND UPDATES

	Phase II C3-002 – Study Protocol	
	Author(s): [name], [name], [name]	Version: v2.1
		Dissemination level: Public

Number	Date	Section of study protocol	Amendment or update	Reason

5. MILESTONES

STUDY SPECIFIC DELIVERABLE	TIMELINE
Draft Study Protocol	September 2023
Final Study Protocol	End of October 2023
Creation of Analytical code	November 2023
Execution of Analytical Code on the confirmed databases	December 2023
Interim Study Report (if applicable)	NA
Draft Study Report	31 st January 2024
Final Study Report	To be confirmed

6. RATIONALE AND BACKGROUND

	Phase II C3-002 – Study Protocol	
	Author(s): [name], [name], [name]	Version: v2.1
		Dissemination level: Public

The research agenda of the Vaccine Monitoring Platform jointly coordinated by EMA and the European Centre for Disease Prevention and Control (ECDC) includes the continuous assessment of COVID-19 vaccine effectiveness.

COVID-19 vaccines were authorised for use in the European Union. These vaccines, and any (future) adapted vaccines, would therefore benefit from post-authorisation studies to provide real world evidence to guide regulatory and vaccination policies. A recent post-authorisation study performed in the Nordic countries, where near real-time data is available, showed that receipt of a bivalent BA4/5 mRNA booster as a fourth dose provides 67.8% protection against COVID-19 related hospitalisation⁴. There is also evidence that effectiveness starts to wane after a few months. For regulatory purposes, such data are especially useful for the most recent variants, including XBB and later.

There is mounting evidence on the occurrence of longer-term outcomes of SARS-CoV-2 infection⁵. This can include very specific outcomes such as cardiovascular events or the incidence of new-onset diabetes, or broader definitions such as the WHO clinical case definition for post COVID-19 condition⁶. Data are needed regarding the COVID-19 vaccines effectiveness at preventing these outcomes. This is pertinent for the most recent COVID-19 variants, but equally important for older variants.

The EMA has therefore requested a study to evaluate the effectiveness of Comirnaty and Spikevax against severe COVID-19 outcomes and post-acute outcomes of SARS-CoV-2 infection.

7. RESEARCH QUESTION AND OBJECTIVES

Research Question

What is the effectiveness of the EMA-authorized COVID-19 vaccines Comirnaty and Spikevax against severe COVID-19 and post-acute outcomes of SARS-CoV-2 infection?

Objective(s)

To generate additional evidence on the effectiveness of COVID-19 vaccines at preventing severe COVID-19 and post-acute outcomes of SARS-CoV-2 infection.

Specifically, this study has 6 objectives:

1. To assess the effectiveness of COVID-19 vaccination for the prevention of severe COVID-19 related outcomes (COVID-19 related hospitalisation or COVID-19 related death)
2. To assess waning of the effectiveness of COVID-19 vaccination for the prevention of severe COVID-19 related outcomes (COVID-19 related hospitalisation or COVID-19 related death)
3. To assess the effectiveness of COVID-19 vaccination for the prevention of all-cause mortality in the 3- and 6-months following discharge for COVID-19 related hospitalisation
4. To assess the effectiveness of COVID-19 vaccination for the prevention of new-onset type 1 Diabetes Mellitus in the 12 months after a SARS-CoV-2 infection
5. To assess the effectiveness of COVID-19 vaccination for the prevention of new-onset type 2 Diabetes Mellitus in the 12 months after a SARS-CoV-2 infection
6. To assess the effectiveness of COVID-19 vaccination for the prevention of cardiovascular events in the 12 months after a SARS-CoV-2 infection

	Phase II C3-002 – Study Protocol	
	Author(s): [name], [name], [name]	Version: v2.1
	Dissemination level: Public	

Table 7.1: Primary and secondary research questions and objective

A. Primary research question: Objectives 1-2

Objective:	To assess the effectiveness and waning of effectiveness of COVID-19 vaccination for the prevention of severe COVID-19 related outcomes
Hypothesis:	NA
Population (mention key inclusion-exclusion criteria):	All subjects aged 12 years and older, with at least 365 days of data availability in the respective database before index date (ID) with 
 • a 3rd-vaccine dose (1st booster dose) of Comirnaty or Spikevax. • at least 365days of data availability in the respective database • at least 90days of time elapsed since the last vaccine dose (i.e. the 3rd vaccine dose or 1st booster) at the time of study inclusion • at least 90days of time elapsed since the last record of a clinical diagnosis of COVID-19 or positive SARS-COV-2 test at the time of study inclusion.
Exposure:	4 th vaccine dose/2 nd booster dose of Comirnaty or Spikevax
Comparator:	No 4 th vaccine dose/2 nd booster dose (only 3 rd dose)
Outcome:	COVID-19 related hospitalisation;COVID-19 related death
Time (when follow up begins and ends):	Follow-up start: at index date of matched 3-dose vaccinated/4-dose vaccinated people after start of roll-out of vaccination programs for 2nd booster dose End of follow-up: End of their observation (i.e. date of data extraction, database availability or death), next vaccine dose or outcome event, whatever comes first.
Setting:	Primary care electronic health records from SIDIAP [Spain], IPCI [The Netherlands] and CPRD GOLD [UK]
Main measure of effect:	Vaccine effectiveness, calculated as 1 - Hazard ratio (HR)

B. Primary research question: Objectives 3

	Phase II C3-002 – Study Protocol	
	Author(s): [name], [name], [name]	Version: v2.1
	Dissemination level: Public	

Outcome:	To assess the effectiveness of COVID-19 vaccination for the prevention of post-acute all-cause mortality in the 3- and 6-months following discharge for COVID-19 related hospitalisation
Hypothesis:	NA
Population (mention key inclusion-exclusion criteria):	All subjects aged 12 years and older, with at least 365 days of data availability in the respective database before index date (ID) with 
 • a 1st-vaccine dose [2nd vaccine dose; 3rd vaccine dose] of Comirnaty or Spikevax. • at least 365days of data availability in the respective database. • at least 90days of time elapsed since the last vaccine dose at the time of study inclusion. • at least 90days of time elapsed since the last record of a clinical diagnosis of COVID-19 or positive SARS-COV-2 test at the time of study inclusion.
Exposure:	2 nd vaccine dose [3 rd vaccine dose; 4 th vaccine dose] of Comirnaty or Spikevax
Comparator:	No 2 nd vaccine dose [3 rd vaccine dose; 4 th vaccine dose] of Comirnaty or Spikevax
Outcome:	All-cause mortality within 3/6months following COVID-19 related hospitalisation
Time (when follow up begins and ends):	Follow-up start: at index date of matched single-vaccinated/ double-vaccinated people [double-vaccinated vs. triple vaccinated; triple vaccinated vs. 4 th dose vaccinated] after start of roll-out of vaccination programs i.e. from 01/01/2021 End of follow-up: End of their observation (i.e. date of data extraction, database availability or death), next vaccine dose or outcome event, whatever comes first.
Setting:	Primary care electronic health records from SIDIAP [Spain], IPCI [The Netherlands] and CPRD GOLD [UK]
Main measure of effect:	
 • Incidence rate for outcomes-100'000 person-years • Vaccine effectiveness against post COVID-19 mortality, calculated as 1 - HR

C. Primary research question: Objectives 4-6

	Phase II C3-002 – Study Protocol	
	Author(s): [name], [name], [name]	Version: v2.1
	Dissemination level: Public	

Outcome:	To assess the effectiveness of COVID-19 vaccination for the prevention of new-onset type 1 Diabetes Mellitus, type 2 Diabetes Mellitus or cardiovascular events in the 12 months after a SARS-CoV-2 infection
Hypothesis:	NA
Population (mention key inclusion-exclusion criteria):	All subjects aged 12 years and older, with at least 365 days of data availability in the respective database before index date (ID) with 
 • a 1st-vaccine dose [2nd vaccine dose; 3rd vaccine dose] of Comirnaty or Spikevax. • at least 365days of data availability in the respective database. • at least 90days of time elapsed since the last vaccine dose at the time of study inclusion. • at least 90days of time elapsed since the last record of a clinical diagnosis of COVID-19 or positive SARS-COV-2 test at the time of study inclusion • no diagnosis of the respective outcome in the patients history
Exposure:	2 nd vaccine dose [3 rd vaccine dose; 4 th vaccine dose] of Comirnaty or Spikevax
Comparator:	No 2 nd vaccine dose [3 rd vaccine dose; 4 th vaccine dose] of Comirnaty or Spikevax
Time (when follow up begins and ends):	Follow-up start: at index date of matched single-vaccinated/ double-vaccinated people [double-vaccinated vs. triple vaccinated; triple vaccinated vs. 4 th dose vaccinated] after start of roll-out of vaccination programs i.e. from 01/01/2021 End of follow-up: End of their observation (i.e. date of data extraction, database availability or death), next vaccine dose or outcome event, whatever comes first.
Setting:	Primary care electronic health records from SIDIAP [Spain], IPCI [The Netherlands] and CPRD GOLD [UK]
Main measure of effect:	
 • Incidence rate for outcomes-100'000 person-years • Vaccine effectiveness against post- acute COVID-19 complications, calculated as 1 - HR

8. RESEARCH METHODS

	Phase II C3-002 – Study Protocol	
	Author(s): [name], [name], [name]	Version: v2.1
		Dissemination level: Public

8.1 Study type and Study Design

STUDY TYPE	STUDY DESIGN	STUDY CLASSIFICATION
Vaccine Effectiveness Studies	New User Cohorts	Complex Study

8.2 Study Setting and Data Sources

This study will be conducted using routinely collected data from 3 databases in 3 European countries. All databases were previously mapped to the OMOP CDM.

1. Clinical Practice Research Datalink (CPRD GOLD), United Kingdom
2. Integrated Primary Care Information Project (IPCI), The Netherlands
3. Sistema d'Informació per al Desenvolupament de la Investigació en Atenció Primària (SIDIAP), Spain

Detailed information on data sources is described in [Table 8.2.1](#).

Database selection

The selection of databases for this study was performed based on data reliability and relevance for the proposed research question among those databases onboarded and available within DARWIN EU. The selected databases fulfil the criteria required for the availability of key information on exposures (i.e. complete recording of vaccines including date and brand), outcomes (except for hospitalization), and covariates, while covering different settings and regions of Europe.

Records on SARS-CoV-2 infection and vaccination will be available in all databases. We have previously published studies showing that these databases can generate reliable evidence on COVID-19 research¹⁻⁷⁻¹⁰. Specifically, the availability of COVID-19 tests results, and linked vaccination records through national/regional immunization program (CPRD, SIDIAP) increased the reliability of the identified study exposures. Information on hospitalization will be available in SIDIAP and IPCI, which provides primary care records with (linked) hospitalization information.

No SARS-CoV-2 variant information from sequencing is available in any of the databases. We will therefore use calendar period with predominance of variants as a proxy for SARS-COV-2 variants in this study.

Information on vaccine products (i.e. monovalent/bivalent booster) are not reliably recorded in the databases, but only the vaccine brand. We will therefore use the number of vaccine doses in combination with vaccine brand for this study.

Potential for future study repetition

This study could be replicated in the future to include additional databases provided those are onboarded for DARWIN EU and fulfill the selection criteria as outlined above.

	Phase II C3-002 – Study Protocol	
	Author(s): [name], [name], [name]	Version: v2
	Dissemination level: Public	

Table 8.2.1. Description of the selected data sources.

Country	Name of Database	Justification for Inclusion	Health Care setting	Type of Data (EHR, claims, registries)	Number of active subjects	Feasibility count of outcome/exposure (if relevant)	Data lock for the last update	Contributing to objectives
United Kingdom	CPRD GOLD	Complete records on SARS-CoV-2 infection, Covid-19 vaccination, and outcome events of interest (excl. hospitalization for COVID-19)	Primary care	EHR	3M	Covid-19: 360,198 Comirnaty: 2,822,947 Spikevax: 311,069	01/2023	1-2 for outcome “COVID-19 related death” only, 4-6
The Netherlands	IPCI	Complete records on SARS-CoV-2 infection, Covid-19 vaccination, and outcome events of interest	Primary care	EHR	1.39M	Covid-19: 941,329 Comirnaty: 1,173,104 Spikevax: 463,315	12/2022	1-6
Spain	SIDIAP	Complete records on SARS-CoV-2 infection, Covid-19 vaccination, and outcome events of interest; Include inpatient admission information.	Primary care + linkage to hospital data	EHR	5.8M	Covid-19: 3,865,976 Comirnaty: 6,548,545 Spikevax: 3,371,395	06/2022	1-6

	Phase II C3-002 – Study Protocol	
	Author(s): [name], [name], [name]	Version: v2
		Dissemination level: Public

Clinical Practice Research Datalink GOLD, United Kingdom (University of Oxford)

The Clinical Practice Research Datalink (CPRD) is a governmental, not-for-profit research service, jointly funded by the National Institute for Health and Care Research and the Medicines and Healthcare products Regulatory Agency, a part of the Department of Health, United Kingdom (UK) (<https://cprd.com>). CPRD GOLD¹¹ comprises computerized records of all clinical and referral events in primary care in addition to comprehensive demographic information and medication prescription data in a sample of UK patients (predominantly from Scotland (52% of practices) and Wales (28% of practices). The prescription records include information on the type of product, date of prescription, strength, dosage, quantity, and route of administration. Data from contributing practices are collected and processed into research databases. Quality checks on patient and practice level are applied during the initial processing. Data are available for 20 million patients, including 3.2 million currently registered patients. Approval for this study was granted via the Research Data Governance Process.

Integrated Primary Care Information Project (IPCI), The Netherlands (Erasmus)

IPCI is collected from electronic health records (EHR) of patients registered with their general practitioners (GPs) throughout the Netherlands.¹² The selection of 374 GP practices is representative of the entire country. The database contains records from 2.8 million patients out of a Dutch population of 17M starting in 1996¹². The median follow-up is 4.7 years. The observation period for a patient is determined by the date of registration at the GP and the date of leave/death. The observation period start date is refined by many quality indicators, e.g. exclusion of peaks of conditions when registering at the GP. All data before the observation period is kept as history data. Drugs are captured as prescription records with product, quantity, dosing directions, strength and indication. Drugs not prescribed in the GP setting might be underreported. Indications are available as diagnoses by the GPs and, indirectly, from secondary care providers but the latter might not be complete. Approval for this study was obtained from the Governance Board¹².

Information System for Research in Primary Care (SIDIAP), Spain (IDIAP Jordi Gol)

SIDIAP is collected from EHR records of patients receiving primary care delivered through Primary Care Teams (PCT), consisting of GPs, nurses and non-clinical staff¹³. The Catalan Health Institute manages 286 out of 370 such PCT with a coverage of 5.6M patients, out of 7.8M people in the Catalan population (74%). The database started to collect data in 2006. The mean follow-up is 10 years. The observation period for a patient can be the start of the database (2006), or when a person is assigned to a Catalan Health Institute primary care centre. Date of exit can be when a person is transferred-out to a primary care centre that does not pertain to the Catalan Health Institute, or date of death, or date of end of follow-up in the database. Drug information is available from prescriptions and from dispensing records in pharmacies. Drugs not prescribed in the GP setting might be underreported; and disease diagnoses made at specialist care settings are not included. Approval for this study was granted by both SIDIAP's Scientific and Ethics Committee.

8.3 Study Period

The study period will start on 01/01/2021 for all databases covering the period where “any variant” was dominant. The end of the study period will be the last available date of data collection for each contributing dataset.

For analyses conducted specifically at the time of predominance of “XBB variant or later dominant” variant, the study period would start on the 01/03/2023, when XBB became the dominant variant. However, this

	Phase II C3-002 – Study Protocol	
	Author(s): [name], [name], [name]	Version: v2.1
		Dissemination level: Public

period is not covered by the data cuts currently onboarded for DARWIN EU®. Analyses will therefore start at the time when vaccine booster programs offering the 4th vaccine dose were rolled out in each country.

Table 8.3.1. illustrates the periods of COVID-19 variant dominance across UK, The Netherlands and Spain.

Table 8.3.1. Periods of variant dominance

	UK	The Netherlands	Spain
Any variant	01/2021 - ongoing	01/2021 – ongoing	01/2021 - ongoing
Alpha and earlier variants	01/01/2021 - 01/06/2021	01/01/2021 – 01/07/2021	01/01/2021 – 01/07/2021
Delta	01/06/2021 – 15/12/2021	01/07/2021– 15/12/2021	01/07/2021– 15/12/2021
Omicron	15/12/2021 – 01/03/2023	15/12/2021 – 01/03/2023	15/12/2021 – 01/03/2023
XBB variant or later dominant	01/03/2023 - ongoing	01/03/2023 - ongoing	01/03/2023 - ongoing

<https://ourworldindata.org/grapher/covid-variants-bar?time=latest&facet=none&country=GBR~ESP~FIN~NOR~NLD>, accessed 15/08/2023

8.4 Follow-up

For all analyses, follow-up time will start from index date.

End of follow-up for each objective will be the end of a person’s observation time (i.e. date of data extraction, database availability or death), the date of their next vaccine dose, fixed duration or the date of the respective outcome event, whatever comes first

Table 8.4.1: Operational Definition of Time 0 (index date) and other primary time anchors

Study population name(s)	Time Anchor Description (e.g. time 0)	Number of entries	Type of entry	Washout window	Care Setting ¹	Code Type	Diagnosis position	Incident with respect to...	Measurement characteristics/ validation	Source of algorithm
1 dose only	Vaccination date 1 st dose	1	incident	All history	OP	RxNorm	n/a	vaccination	n/a	n/a
Complete primary vaccination course (2 doses)	Vaccination date 2 nd dose	1	n/a	21days	OP	RxNorm	n/a	n/a	n/a	n/a
3rd dose (monovalent or adapted/bivalent)	Vaccination date 3 rd dose	1	n/a	90days	OP	RxNorm	n/a	n/a	n/a	n/a
4th dose (monovalent or adapted/bivalent)	Vaccination date 4 th dose	1	n/a	90days	OP	RxNorm	n/a	n/a	n/a	n/a
4th dose (any monovalent)	Vaccination date 4 th dose	1	n/a	90days	OP	RxNorm	n/a	n/a	n/a	n/a
4th dose, (any adapted/bivalent boosters)	Vaccination date 4 th dose	1	n/a	90days	OP	RxNorm	n/a	n/a	n/a	n/a

OP = outpatient, n/a = not applicable

	Phase II C3-002 – Study Protocol	
	Author(s): [name], [name], [name]	Version: v2
		Dissemination level: Public

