8.5 Study Population with inclusion and exclusion criteria

The source population will comprise all subjects aged 12 years and older, with at least 365 days of data availability in the respective database before index date (ID) [ID defined as the date of the “latest” vaccine dose administered] AND data availability from 12/2020 onwards (i.e. the time when the roll-out of the vaccination campaign started) in the respective database will be included.

People will then be matched 1:1 based on the number of vaccines doses they received [exposure], with their matched counterparts having 1 vaccine dose less at the time of matching. Based on the index date of matched counterparts, the following inclusion criteria will be applied:

- At least 365 days of data availability in the respective database
- At least 90days of time elapsed since the last vaccine dose for >2 doses), at least 21days of time elapsed since the last vaccine dose for 2 doses and no previous vaccine dose recorded for 1st dose).
- At least 90days of time elapsed since the last record of a clinical diagnosis of COVID-19 or positive SARS-COV-2 test.

For analyses where diabetes mellitus or cardiovascular events are assessed as post-acute COVID-19 complications, people must not have had a record of the outcome within 365days before their index date for cardiovascular events, and no record anytime before index date for diabetes.

Operational definitions of Inclusion and Exclusion Criteria are provided in [Tables 8.5.1](#) and [8.5.2](#).

	Phase II C3-002 – Study Protocol	
	Author(s): [name], [name], [name]	Version: v2
	Dissemination level: Public	

Table 8.5.1. Operational Definitions of Inclusion Criteria

Criterion	Details	Order of application	Assessment window	Care Settings ¹	Code Type	Diagnosis position ²	Applied to study populations:	Measurement characteristics/validation	Source for algorithm
Observation period of 365day prior entry (all cohorts)	Study participants will be required to have 365 days prior history observed before contributing observation time	before	[-365, 0]	n/a	n/a	n/a	All individuals within the selected databases	n/a	n/a
Covid-19 vaccinated: 1 dose only	Exactly 1 Comirnaty/Spikevax vaccination record	after	n/a	OP	RxNorm	n/a			
Covid-19 vaccinated: Completed primary vaccination course	Exactly 2 vaccination records, with the latest being Comirnaty/Spikevax and at least 21days later than the 1st dose.								

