Large-scale propensity scores (PS) will be computed to estimate the probability of receiving a 4th vaccine dose. Covariates to be included in the large-scale PS will be selected from co-medications and comorbidities recorded prior to cohort-specific index dates. Among those, covariates with a prevalence below 0.5% in the study population will be omitted. Logistic regression with LASSO regularization will then be used for variable selection. The list of selected covariates will be manually screened by 2 epidemiologists/clinical domain experts to exclude potential instrumental variables.

The same procedure will be conducted in the calendar week after, with previously non-boostered people being allowed to be included in the booster cohort once they change exposure status. Non-boostered people can only be matched once to a booster counterpart during the whole study. With matching, non-boostered counterparts will be assigned the date of when the booster counterpart received their 4th vaccine dose as their “final” index date (index date for the matched pair).

All booster and matched non-boostered people from sequential weekly matching will be combined into the booster and non-boostered cohort for subsequent analyses. The study inclusion and sequential matching process is illustrated in [Figure 8.8.3.1](#) below.

[figure not shown]

	Phase II C3-002 – Study Protocol	
	Author(s): [name], [name], [name]	Version: v2.1
	Dissemination level: Public	

Figure 8.8.3.1 Study inclusion and sequential matching process

	Phase II C3-002 – Study Protocol	
	Author(s): [name], [name], [name]	Version: v2.1
		Dissemination level: Public

Follow-up

In the matched cohorts, people will be followed up from their index date until the earliest of

- End of their observation (i.e. date of data extraction, death)
- 2nd booster vaccination for unvaccinated group, 3rd booster for vaccinated group etc.
- COVID-19 related hospitalization or death, with outcome date being defined as the date of first COVID-19 diagnosis/positive test related to hospitalization or death.

Follow-up will be censored for the matched pair if one counterpart is censored, but not if one counterpart experiences the outcome.

Outcomes

The outcomes are defined in detail in section 8.6.2.

COVID-19 related hospitalization will be assessed for SIDIAP and IPCI. COVID-19 related death will be assessed for CPRD, IPCI and SIDIAP.

Statistical Analyses

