8.8.4 Objective 3: Vaccine effectiveness to prevent COVID-19 related mortality

Objective 3 will assess vaccine effectiveness to prevent all-cause mortality in the 3 months/6 months after discharge from a COVID-19 hospitalisation. This objective will be assessed for SIDIAP and IPCI only, as no information on hospitalisation are available in CPRD.

	Phase II C3-002 – Study Protocol	
	Author(s): [name], [name], [name]	Version: v2.1
		Dissemination level: Public

The following comparisons will be conducted:

- 1st dose vaccinated vs. 2nd dose vaccinated [cohort 5 vs. 6]
- 2nd vaccinated vs. 3rd dose vaccinated [cohort 6 vs. 7]
- 3rd dose vaccinated vs. 4th dose vaccinated [cohort 7 vs. 8]

Study population

The study populations will be derived similar to the inclusion process outlined for objectives 1-2 above, including sequential matching. The following inclusion criteria will be applied:

- At least 365 days of data availability in the respective database
- At least 90days of time elapsed since the previous vaccine dose for the 3rd or 4th vaccine dose
- At least 21days of time elapsed since the previous vaccine dose for the 2nd vaccine dose
- At least 90days of time elapsed since the last record of a clinical diagnosis of COVID-19 or positive SARS-COV-2 test.

Outcomes

For contextualization, we will assess vaccine effectiveness to prevent COVID-19 hospitalization for the mentioned comparisons. The primary study outcome will be COVID-19 hospitalization followed by death within 3 or 6 months from discharge.

Statistical Analyses

Vaccine effectiveness analyses for COVID-19 related mortality following hospital discharge:

Incidence rates will be calculated for the matched cohorts and both outcomes. Cox proportional hazard models will be calculated for each outcome to provide HR. Follow-up will start at index date, i.e. the date of vaccination with respective new dose for matched pairs.

Negative control outcomes will be used as an additional measure to measure potential residual confounding. In the scenario of potential unmeasured confounding being detected by NCO, empirical calibration²⁵ for HR might be considered to minimise bias.

Kaplan Meier plots and/or cumulative incidence plots will be used to illustrate survival analyses.

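### Objective 3 ends follow-up at the next vaccine dose even after a COVID-19 admission; if an admission postpones a person's own next dose, this censoring is informative and can bias the post-discharge mortality hazard ratio

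*Protocol*

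**What the plan says.** Objective 3 supplies primary outcomes 3 and 4. Section 8.8.4 defines the event: "The primary study outcome will be COVID-19 hospitalization followed by death within 3 or 6 months from discharge". The clock starts at vaccination, not at discharge: "Follow-up will start at index date, i.e. the date of vaccination with respective new dose for matched pairs".

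Section 8.4 lists the ends of follow-up for each objective, among them "the date of their next vaccine dose, fixed duration or the date of the respective outcome event, whatever comes first". Table 7.1 B, specific to Objective 3, also stops at "next vaccine dose or outcome event, whatever comes first". Both are written person by person. Table 8.6.2.1 enters the date of death as the detail for all-cause mortality.

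Two rules in section 8.8.3 are written for Objectives 1-2. One concerns pairs: "Follow-up will be censored for the matched pair if one counterpart is censored, but not if one counterpart experiences the outcome". The other concerns dating: the outcome is COVID-19 hospitalisation or death, "with outcome date being defined as the date of first COVID-19 diagnosis/positive test related to hospitalization or death". Section 8.8.4 restates neither. Its only link is "The study populations will be derived similar to the inclusion process outlined for objectives 1-2 above, including sequential matching".

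Section 8.5 matches people 1:1, "with their matched counterparts having 1 vaccine dose less at the time of matching", so the comparator's next dose is the dose under study. The 12-month follow-up requirement in section 8.8.5 covers outcomes 5 to 7 only, and section 8.8.6 plans no sensitivity analyses.

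**The concern.** The event has two steps, an admission and then a death weeks or months later. Under the rule as written, a next dose taken between the two removes the death from the analysis. That is harmless if doses arrive independently of the admission. It is not harmless if an admitted person's own next dose is put off, because whether follow-up stays open then depends on having taken the first step towards the event. Matching at time zero cannot repair this, since the dependence arises afterwards.

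The mechanism depends on which censoring rule applies:

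- **Pair censoring.** An admitted comparator postpones its own dose and the pair stays open. When the newer-dose member is admitted, the unaffected comparator is vaccinated as usual and the pair closes before the death can count. Deaths are then lost more often in the newer-dose arm.
- **Person-level censoring.** Uninfected comparators leave at their next dose while admitted comparators stay. The comparator risk set is enriched with people close to the event.

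Both push the hazard ratio the same way, towards apparent effectiveness when comparators take their next dose faster. At stake is the validity of two primary outcomes, with no planned analysis that would reveal the problem.

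**Working it through.** The protocol gives no event count, uptake rate or power for Objective 3, so there is no figure of its own to reproduce. The question is what hazard ratio the rule returns when the true value is 1.

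**Closed form.** All inputs here are assumptions. λ and μ are the monthly next-dose rates in the comparator and newer-dose arms, D is the postponement of a person's own dose after admission (months), and s is time from admission to death, uniform with density f(s) on 0 to 3 or 0 to 6 months. The hospital stay is ignored.

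- Pair censoring: HR = ∫f(s)·exp(−λs − μ·max(0, s−D))ds ÷ ∫f(s)·exp(−μs − λ·max(0, s−D))ds
- Person-level censoring: HR = ∫f(s)·exp(μ·min(s, D))ds ÷ ∫f(s)·exp(λ·min(s, D))ds

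Worked case: λ = 0.2, μ = 0.02, D = 3, 3-month window.

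- Pair: newer arm (1 − e^−0.6)/0.6 = 0.752 of deaths counted; comparator (1 − e^−0.06)/0.06 = 0.971; HR = 0.752/0.971 = 0.77.
- Person: newer arm (e^0.06 − 1)/0.06 = 1.031; comparator (e^0.6 − 1)/0.6 = 1.370; HR = 1.031/1.370 = 0.75.

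With μ = 0.02, as λ goes from 0.1 to 0.3:

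| Delay D (months) | Censoring | 3-month HR | 6-month HR |
|---|---|---|---|
| 0 | either | 1.00 | 1.00 |
| 0.5 | pair | 0.96 to 0.88 | 0.96 to 0.88 |
| 1 | pair | 0.94 to 0.80 | 0.93 to 0.79 |
| 3 | pair | 0.89 to 0.68 | 0.84 to 0.58 |
| 3 | person | 0.88 to 0.64 | 0.83 to 0.51 |

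Varying the other assumptions:

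- λ = μ = 0.1 gives 1.00 at any delay.
- λ = 0.1, μ = 0.2, D = 3, pair censoring gives 1.15 (3 months) and 1.21 (6 months).
- If deaths cluster early (decaying at rate 1 per month), the most extreme 6-month values move from 0.58 to 0.79 (pair) and from 0.51 to 0.74 (person).

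**Simulation.** Four million matched pairs, true HR 1, Cox model. Assumed: 3% admitted per 180 days and 10% dead 90 days after discharge. The window is 3 months unless stated.

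| Scenario | Censoring | No delay | 30 days | 90 days |
|---|---|---|---|---|
| Comparator's dose dominates (median 90 days, 20% never; newer arm from day 180) | pair | 1.01 | 0.93 | 0.88 |
| Same, 6-month window | pair | 1.00 | 0.93 | 0.84 |
| Same, 3-month window | person | 1.03 | 0.94 | 0.91 |
| Newer arm has no next dose in the data | pair | 0.98 | 0.89 | 0.82 |
| Fast comparator uptake (median 30 days) | pair | 1.01 | 0.88 | 0.81 |
| Mixed drivers | pair | 0.97 | 1.02 | 1.04 |
| Newer arm's dose dominates | pair | 1.00 | 1.13 | 1.38 |

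In the first scenario with a 30-day delay, pair censoring removes 17.6% of comparator deaths and 23.8% of newer-dose deaths. Person-level censoring removes 10.0% and 6.4%: the comparator arm loses more, yet the HR is still 0.94.

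**Which arm's dose is likely to dominate.** Section 8.8.4 restricts Objective 3 to SIDIAP and IPCI. Table 8.2.1 gives data locks of 06/2022 and 12/2022, and the abstract starts the 4th-dose period on 01/08/2022. For 2nd versus 3rd dose, the newer arm's next dose is a 4th dose, which on those dates leaves at most about five months in IPCI and none in SIDIAP. For 3rd versus 4th dose it is a 5th dose. Next doses in the newer arm should therefore be scarce in these two comparisons. Late 1st-versus-2nd-dose pairs are different, because 3rd doses can fall well inside the data.

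**With the fix.** Dose censoring up to the first admission in the pair, then death counted over the fixed window: the newer-to-older death ratio was 0.98 to 1.02 in every scenario rerun, including the one where the newer arm's dose dominates, at delays of 30 and 90 days (standard error of the log ratio about 0.01).

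**The case against.** The strongest reply is that the driver is not in the documents. Nothing says an admission delays the next dose; the 90-day infection-free interval is a criterion for entering the study, not a dosing rule. With no delay there is no bias. This stands, and the point is conditional on it. No delay at all is, however, the limiting case: it needs people in hospital or just discharged to be vaccinated at the same rate as everyone else.

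A reader might infer that deaths are always cut off more often in the newer-dose arm. The text does not support that. It needs pair censoring, which section 8.8.3 states for Objectives 1-2 and which reaches Objective 3 only through a sentence about deriving study populations. Under the person-level wording of section 8.4 and Table 7.1 B the comparator arm can lose more deaths, though the hazard ratio moves the same way.

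A reader might also infer that Objective 3 will show false effectiveness, possibly above 40%. The sign depends on which arm takes its next dose faster and can reverse. Values that low need 30% monthly uptake in comparators against 2% in the newer arm, a three-month delay and deaths spread evenly over six months.

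Finally, the date of death in Table 8.6.2.1 describes generic all-cause mortality, and no date is given for the Objective 3 composite. If the diagnosis date were adopted and deaths followed regardless of later doses, the problem would vanish. That is true, but the protocol says neither, while its stated end of follow-up is explicit and has no exception. This is more than a detail left for an analysis plan.

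**Conclusion.** The point holds in conditional form. The protocol states a next-dose censoring rule that does not suit a delayed two-step outcome, and does not carry over the dating rule that would protect it. If an admission postpones a person's own next dose, the censoring is informative. The bias is probably towards false effectiveness for 2nd versus 3rd and 3rd versus 4th dose, given the listed data locks, and less predictable for 1st versus 2nd dose.

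For delays of 0.5 to 3 months with the comparator's dose dominant, the null hazard ratio is roughly 0.8 to 0.96, a spurious effectiveness of about 4% to 20%. Lower values need a long delay combined with fast and very unequal uptake. Uptake, delay and timing of deaths are all assumed, so these figures show plausible size and do not predict the result. A primary outcome exposed to a bias of this order, with no sensitivity analysis, justifies a change before the analysis is run.

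**What to change.** In section 8.4, Table 7.1 B and Table 8.6.2.1, state for Objective 3 that:

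1. next-dose censoring, and pair censoring if it is meant to apply, operate only up to the qualifying COVID-19 infection or admission;
2. once that point is reached, death is ascertained to 3 and 6 months after discharge whatever later dose either pair member receives;
3. the composite event is dated at the COVID-19 diagnosis or admission, following section 8.8.3, with the same date used as the cut-off in item 1;
4. only admissions whose full 3- or 6-month window ends before the end of data are counted.

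Section 8.8.4 should also say outright whether pair censoring governs Objective 3. Report the next-dose-censored analysis as a sensitivity analysis in section 8.8.6.

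The cost is protocol wording and a change to the outcome-building code. There are two downsides: doses received after discharge become part of the post-discharge course, and the most recent admissions are dropped.
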